4.0 Study Endpoints*

Primary end point:

To assess the technology and its ability to see blood supply in the subscapularis tendon before takedown and after employed repair. The benchmark for this is the rise and fall of fluorescence signal approximately 10-40 seconds after injection. Given our experience in DCE-FI for bone fractures, it will be more or less self-evident whether the DCE-FA signal is sufficient for further analysis.

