2.0 Objectives

The purpose of this pilot study is to evaluate the feasibility of open, wide-field imaging of indocyanine green ingress and egress during total shoulder arthroplasty.

The long-term goal of this work is to use DCE-FA for the assessment of subscapularis tendon perfusion and to determine potential relationships between perfusion and patient reported outcomes and subscapularis failure.

Primary Research Question:

To what degree does the relative perfusion of the subscapularis tendon—measured using DCE-FI—change after tenotomy vs peel technique and subsequent intra-operative repair?

Hypothesis: Perfusion of the subscapularis tendon will be reduced from baseline after tenotomy and peel techniques during shoulder arthroplasty.

Secondary Question:

Does DCE-FI with indocyanine green, used in a real time, intra-operative setting, highlight technique-dependent variations in subscapularis tendon perfusion during shoulder arthroplasty?

Aim: To determine if intra-operative ICG administration during shoulder arthroplasty can be coupled with an intra-operative surgical fluorescence detection device to determine alterations in subscapularis tendon perfusion before and after repair using peel and tenotomy takedown techniques for a deltopectoral approach.

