Each subscapularis takedown technique requires repair at the conclusion of the procedure when performing shoulder arthroplasty. Repair is crucial for proper force coupling of the shoulder to keep the humeral head implant centered on the glenoid component (Shields *et al.*, 2017). Takedown is still performed in a reverse total shoulder arthroplasty but repair is not required to maintain stability. Each takedown technique is reliant on either tendon to tendon, tendon to bone, or bone to bone interface for healing. Failure of the subscapularis tendon repair can result in pain, instability, decreased functional outcomes and ultimately the need for revision surgery (Choate *et al.*, 2018). Subscapularis tendon failure can sometimes be asymptomatic, however it can also be symptomatic and present with the aforementioned signs. Subscapularis failure rates may approach 50% in long term studies although symptomatic cases likely occur in less than 1% of total shoulder arthroplasties (Entezari *et al.*, 2020). Due to the devastating impact on patients with symptomatic subscapularis failure, there is interest in investigating which subscapularis takedown technique produces the best outcomes. Prior randomized controlled trials as well as systematic reviews have previously been conducted looking at these different takedown techniques, but demonstrated no statistically significant difference in primary endpoints of subscapularis strength at various time endpoint and no statistically significant difference in patient reported outcomes (Lapner *et al.*, 2020). These prior studies did not evaluate subscapularis perfusion post repair, adequate perfusion is necessary for healing to occur with any subscapularis takedown technique.

The takedown method of the subscapularis has previously been shown to have no statistically significant differences with regards to strength, or patient reported outcomes, however if there was a difference noted in tendon perfusion post repair this may provide rationale to choose one technique over another as improved perfusion may correlate to lower risk of repair failure. As this study aims to monitor subscapularis perfusion pre and post repair, the two techniques that the involve the tendon itself for healing will be utilized, peel and tenotomy.

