The indocyanine green based DCE-FI will NOT be used to guide treatment or patient care. The data acquired using the SPY Elite or SPY PHI or EleVision will be anonymized and exported to a secure PC for additional analysis and processing. The analysis techniques will be more sophisticated than the current commercial system, and involve a correction for the patient-specific arterial input function (AIF) (Elliott *et al.*, 2020)—the cardiac and circulatory variations that can modify the time and manner in which the ICG dye arrives in the imaging field-of-view.

Indocyanine green (ICG) is a well-studied water soluble, light absorbing tracer that has been used in other capacities to help quantify tissue perfusion during

PROTOCOL TITLE: Pilot feasibility study of dynamic contrast-enhanced fluorescence imaging to guide total shoulder arthroplasty approach

surgery. ICG is able to be injected into a patient intravenously and subsequently circulate systemically while bound to albumin, quickly undergoing hepatic metabolism in just several minutes (Faybik and Hetz, 2006). The concentration of ICG in specific tissue is able to be quantified as a surrogate for tissue perfusion. ICG due to its IV administration and quick metabolism is able to help quantify perfusion in real time, such as intra-operatively (Lutken *et al.*, 2021). Systemic reviews as well as case studies, most commonly in plastic surgery, have been performed showing its utility to determine adequate or inadequate perfusion in downstream tissue in situations where microanastomoses are performed, such as with flaps (Krishnan *et al.*, 2005) and in hand surgery (Li *et al.*, 2018). Other studies have also been conducted showing the ability to use ICG as a surrogate for tissue perfusion in the achilles paratenon in humans and in rabbits who had undergone rotator cuff repair to determine tissue perfusion after different types of repair. The use of ICG imaging in orthopaedic surgery is relatively nascent, and our institution (Gitajn *et al.*, 2020) as well as other collaborators (Sepehri *et al.*, 2021) have demonstrated its promise in these applications.

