5.0 Study Intervention/Investigational Agent

5.1 Description:

This study is neither a drug nor a device trial. Patients will be administered FDA approved ICG through intravenous injection and imaged by a FDA approved surgical fluorescence imaging device (Spy Elite or SPY PHI or Medtronic EleVision) which is 0.5 meter away from the subject. Both ICG fluorescence and the imaging system have been used for routine clinical practice for many years. ICG fluorescence imaging utilizes intravenously injected ICG, which is a fluorescent dye that is FDA-approved for clinical use, illuminated with near-infrared light. The ICG dye is indirectly activated and the dynamic fluorescence due to tendon perfusion can be captured by a video rate imaging system. The subscapularis takedown technique will alternate between tenotomy and peel for every other patient taken to the operating room. There is no reason intraoperatively to choose one technique over the other and therefore this puts

PROTOCOL TITLE: Pilot feasibility study of dynamic contrast-enhanced fluorescence imaging to guide total shoulder arthroplasty approach

the patient at no added risk. If the surgeon feels that neither of these techniques are appropriate for the treatment of the patient then the patient will not be approached for enrollment.

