A Pulse dye densometer (PDD; in-house developed), similar to a pulse oximetry probe, which is used clinically both in the operating room, in inpatients as well as outpatients to assess oxygen saturation. This is completely non-invasive. In the context of this study the pulse dye densometer collects data on the ICG injection parameters so that the kinetic curves can be normalized to injection-related differences. The PDD will be placed on the patient's finger to acquire an arterial blood input function during ICG injection.

After the subscapularis tendon is visualized during the surgical approach, 0.1 mg/kg ICG will be injected intravenously. Video rate ICG fluorescence images will be acquired 20 seconds before and 4 minutes after ICG injection. This process will be repeated towards the end of the procedure after the subscapularis is repaired, but prior to skin closure.

ICG will be administered by an anesthetist in the operating room. Patients are under the care and observation of the anesthesia and surgical teams during this time. Postoperatively, patients are transferred to the Post-Anesthesia Care Unit (PACU) where they are monitored

PROTOCOL TITLE: Pilot feasibility study of dynamic contrast-enhanced fluorescence imaging to guide total shoulder arthroplasty approach

continuously by nursing staff supervised by anesthesiologists. During this entire time vital signs (including temperature, pulse, respiratory rate and blood pressure) are collected as standard of care. All clinical data will be reviewed for adverse events for a period of 30 minutes post-injection.

Day of surgery Procedures	Pre-Infusion	0-30 minutes post-infusion
Pulse	X	X
Blood Pressure	X	X
Temperature	X	X
Respiratory Rate	X	X
Adverse Events		X

Study patients will be seen per usual protocol for wound assessment and general health assessment after their shoulder arthroplasty at approximately 4 weeks post operatively.

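### The feasibility benchmark in Section 4.0 is applied after repair to the same tendon signal that serves as the perfusion outcome, so a correctly imaged tendon with little or no flow would miss it just as failed imaging would

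*Protocol*

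**What the plan says.** Section 4.0 of the protocol gives the primary endpoint as the technology's "ability to see blood supply in the subscapularis tendon before takedown and after employed repair". It then fixes a single criterion: "The benchmark for this is the rise and fall of fluorescence signal approximately 10-40 seconds after injection". Nothing confines that criterion to the first acquisition. How the signal is judged is left to experience with bone fractures: "it will be more or less self-evident whether the DCE-FA signal is sufficient for further analysis".

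Other sections give the same signal a second role. Section 5.1 says that "the dynamic fluorescence due to tendon perfusion can be captured by a video rate imaging system". Section 3.0 says: "The concentration of ICG in specific tissue is able to be quantified as a surrogate for tissue perfusion". The primary research question in Section 2.0 is how far this perfusion changes after takedown and repair, and the hypothesis is: "Perfusion of the subscapularis tendon will be reduced from baseline after tenotomy and peel techniques during shoulder arthroplasty".

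Section 6.0 repeats the injection and the video after repair. It also places a PDD on the finger "to acquire an arterial blood input function during ICG injection". Sections 6.0 and 6.2 give that trace the task of normalising the kinetic curves. Section 4.0 does not mention it.

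**The concern.** A feasibility criterion should depend on whether the method works and not on what the method finds. Before takedown these coincide well enough: Section 10.0 admits only patients with an intact subscapularis, so a missing curve there points to the technology. After repair they separate. The surgery may itself have reduced the blood supply, and measuring that reduction is the purpose of the study.

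If a repaired tendon has lost nearly all its flow, a flat curve is the right answer, yet it does not meet the benchmark. Taken alone, the post-repair benchmark then gives the same result for loss of flow as for failure of imaging. The estimate of perfusion loss is also at stake if the judgement of sufficiency is used to decide which acquisitions are analysed. That matters because Section 3.0 says that "if there was a difference noted in tendon perfusion post repair this may provide rationale to choose one technique over another".

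**Working it through.** The protocol states no success proportion, power or no-flow rate, so there is no figure to reproduce. The check is first one of reading, then an illustration under stated assumptions.

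**1. Reading.** The endpoint sentence in Section 4.0 covers both time points, and the benchmark sentence refers back to it. Sections 3.0 and 5.1 equate the dynamic tendon signal with perfusion. Section 2.0 takes the post-repair perfusion as the outcome. So one post-repair curve answers two questions: whether imaging worked, and whether the tendon was perfused. No amplitude limit is set, so a reduced but visible rise and fall passes. Only absent or nearly absent flow fails.

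**2. Effect on the benchmark, whichever way sufficiency is read.** Inputs: n = 10 (Sections 1.0 and 12.0); k tendons without post-repair flow (assumed); imaging successful in all 10 (assumed). Benchmark met = (10 − k)/10, with Clopper-Pearson 95% limits.

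| k | Benchmark met after repair | Exact 95% CI | Imaging worked |
|---|---|---|---|
| 0 | 10/10 | 69.2% to 100% | 10/10 |
| 1 | 9/10 | 55.5% to 99.7% | 10/10 |
| 2 | 8/10 | 44.4% to 97.5% | 10/10 |
| 3 | 7/10 | 34.8% to 93.3% | 10/10 |

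Put as a rate: if a share q of repaired tendons has no visible flow and imaging is perfect, the chance that all 10 meet the benchmark is (1 − q)^10. This is 0.60, 0.35, 0.11 and 0.03 for q = 5%, 10%, 20% and 30%. Under these assumptions the apparent post-repair feasibility is 1 − q, a property of the tendons and not of the device.

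**3. Effect on the estimated loss, only if sufficiency is applied to each acquisition and flat curves are left out.** Let r be the post/pre ratio in the remaining tendons (assumed). True mean loss = 1 − (10 − k)r/10. Reported mean loss = 1 − r.

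| k | True loss, r = 0.6 | Reported | True loss, r = 0.8 | Reported |
|---|---|---|---|---|
| 0 | 40% | 40% | 20% | 20% |
| 1 | 46% | 40% | 28% | 20% |
| 2 | 52% | 40% | 36% | 20% |
| 3 | 58% | 40% | 44% | 20% |

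Between techniques, with 5 patients each and r = 0.6:

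- One no-flow tendon in one technique: 4 × 0.6/5 = 0.48 against 0.60, a difference of 0.12.
- Two in the same technique: 3 × 0.6/5 = 0.36 against 0.60, a difference of 0.24.
- One in each: 0.48 against 0.48, no difference.

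With flat curves omitted, the comparison is 0.60 against 0.60 every time.

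**4. The opposite error.** Counting every flat curve as no flow is not safe either. If u tendons with a true ratio of 0.6 are merely obscured and are entered as zero, the loss becomes 1 − (10 − u) × 0.6/10. This is 46% for u = 1 and 52% for u = 2, against a true 40%. A fix therefore needs a condition that the tendon was in view.

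**The case against.** The strongest reply is that the study already collects what is needed to tell the two causes apart. Each patient is imaged before takedown with the same procedure, and the PDD records the arrival of dye. A clear baseline curve, a normal PDD trace and a flat post-repair curve together point to lost flow or an obscured view, not to failed dye delivery. This stands. A reader might infer that a poor post-repair result could not be interpreted at all, and the documents do not support that. What is missing is any role for these data in the benchmark.

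Second, Section 4.0 writes no pass count and no go/no-go rule, so a formal verdict against the technology does not follow. That also stands. The point is that the stated benchmark is missed, not that a written rule would declare failure.

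Third, the hypothesis is reduced perfusion, not absent perfusion. This is correct, and it limits the problem to near-total loss. It does not remove it, because the study is meant to find out how far perfusion falls.

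Fourth, a reader might infer that flat curves will be dropped and the estimated loss biased. The protocol contains no such exclusion. Section 14.0 removes patients whose imaging cannot be completed, which is different from a completed video without signal. The bias figures are therefore conditional, and detailed handling of such curves could properly sit in an analysis plan. The benchmark itself cannot be left there, because the protocol fixes it.

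Finally, whether blood supply can be seen after repair is a legitimate feasibility question. It should be kept and reported, not replaced.

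**Conclusion.** The point holds in a limited form. Section 4.0 uses one tendon-signal benchmark at both time points, and after repair that signal is also the perfusion outcome. A correctly imaged tendon with absent or nearly absent flow would miss the benchmark in the same way as failed imaging.

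The size is unknown. In the illustration, one to three such tendons among 10 would move the post-repair result from 10/10 to between 9/10 and 7/10 with perfect imaging. If no tendon loses nearly all its flow, nothing changes. Bias of the estimated loss toward zero, and a hidden technique difference, arise only if sufficiency is judged per acquisition and flat curves are then omitted; their size depends on the assumed k and r.

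This should be fixed before data are collected: the criterion is stated and poorly chosen, and the correction is cheap. Confidence is medium, because the harm depends on an event whose frequency the protocol does not give.

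**What to change.** Amend Section 4.0 as follows.

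- Judge the technology's ability to detect a tendon signal on the pre-takedown acquisition. The 20 seconds of video before injection can supply the noise reference.
- For the post-repair acquisition, define technical success by three conditions: video completed, tendon in view (region marked on the recording before its curve is read), and dye arrival on the PDD trace.
- Still report post-repair tendon visibility as x/10 beside technical success, with an exact interval, and read it against the patient's own baseline curve.
- State that technically successful post-repair acquisitions stay in the perfusion analysis whatever their tendon signal. Show results with and without any in which the tendon may have been obscured.

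The cost is a few sentences and slightly more analysis of video and PDD data already planned, with no new procedure or patients. The drawback is that some flat curves will stay ambiguous, because the PDD shows systemic dye arrival and not an unobstructed tendon. With 10 patients, the results with and without those curves may differ visibly.

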12.0 Local Number of Subjects

All 10 patients will be enrolled at this facility by the primary surgeon. This is a modest number of subjects to allow us to properly evaluate the feasibility of evaluating subscapularis tendon perfusion by two different takedown techniques in shoulder arthroplasty.

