14.0 Withdrawal of Subjects*

Participants will be removed from the protocol if:

- 1) Concern for subscapularis tendon tear or insufficiency occurs.
- 2) The subject withdraws consent.

PROTOCOL TITLE: Pilot feasibility study of dynamic contrast-enhanced fluorescence imaging to guide total shoulder arthroplasty approach

- 3) The subject has an occurrence of a significant clinical event that precludes proceeding with surgery.
- 4) Imaging cannot be completed for any reason

If a participant is withdrawn from the protocol, the PI will mark the data of this subject as "withdrawn" and will add a detailed explanation about the cause of withdrawal in the database.

For subjects who withdraw after the intraoperative imaging, but prior to their first post operative appointment, we will follow-up to see if they still complete their clinical follow up at the 1-month interval, and provide them an opportunity to report any adverse events. We will acquire their follow up results to include these subjects in the statistical analysis portion that only involves the intraoperative image data and infection status.

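### The primary feasibility endpoint has only a qualitative benchmark, leaves signal sufficiency to the team's impression, and sets no study-level result that would count against feasibility

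*Protocol*

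**What the plan says.** Protocol Section 1.0 makes feasibility of the imaging the primary objective. Section 4.0 states the endpoint: "To assess the technology and its ability to see blood supply in the subscapularis tendon before takedown and after employed repair". The next sentence gives the yardstick: "The benchmark for this is the rise and fall of fluorescence signal approximately 10-40 seconds after injection". The section then appeals to the team's experience with bone fractures and concludes that "it will be more or less self-evident whether the DCE-FA signal is sufficient for further analysis".

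Section 12.0 justifies the 10 patients in words only: "This is a modest number of subjects to allow us to properly evaluate the feasibility of evaluating subscapularis tendon perfusion". Section 6.0 describes the recording: "Video rate ICG fluorescence images will be acquired 20 seconds before and 4 minutes after ICG injection", repeated after the repair. An arterial input function is recorded as well: "The PDD will be placed on the patient's finger to acquire an arterial blood input function during ICG injection". Section 14.0 lists among its grounds for removal from the protocol: "Imaging cannot be completed for any reason". Such a participant's data are marked as withdrawn and the cause is entered in the database.

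**The concern.** The benchmark gives a shape and an approximate time but no size. It does not say how far the signal must rise above background, how far it must fall, or in which part of the field. The sentence after it passes the remaining decision to impression, calibrated on bone rather than tendon. Two people viewing the same faint or noisy recording could classify it differently, and both would be within the protocol.

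At study level nothing is fixed: no count out of 10 is tied to a conclusion, and there is no commitment to report a proportion with its uncertainty. The removal rule compounds this. A patient in whom imaging could not be completed is direct evidence about feasibility, yet may drop out of the figure that measures it. At stake is whether another reader could reproduce the primary result, and whether it reflects every patient in whom imaging was tried.

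**Working it through.** **1. What is fixed and what is open.** The 10 patients come with no derivation, precision target or success threshold, so there is no figure of the plan's own to reproduce. The text can be sorted as follows.

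| Element | Protocol |
|---|---|
| Shape and timing of signal | Stated (Section 4.0), approximate |
| Size of rise over background; size of fall | Not stated |
| Who judges; knowledge of technique | Not stated |
| How the two recordings combine | Not stated |
| Number of 10 that counts for or against feasibility | Not stated |
| Status of incomplete imaging in the endpoint | Not stated (Section 14.0 removes the participant) |

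**2. Can the planned recording support a computed criterion?** I read Section 6.0 as continuous video from 20 s before to 4 min after each injection: 20 + 240 = 260 s. The benchmark window is 40 − 10 = 30 s and lies wholly inside it. The pre-injection part gives 20 one-second means per recording, from which that recording's own background mean and SD can be computed. No new data are needed.

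**3. Effect of the denominator.** Assume f of 10 patients cannot be imaged and all others succeed. The exact (Clopper-Pearson) 95% limits for x of n are:

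- lower = Beta⁻¹(0.025; x, n − x + 1)
- upper = Beta⁻¹(0.975; x + 1, n − x)
- for x = n, the lower limit reduces to 0.025^(1/n) and the upper limit is 100%.

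| f | All 10 counted | 95% CI | Failures removed | Lower limit |
|---|---|---|---|---|
| 1 | 9/10 = 90% | 55.5% to 99.7% | 9/9 = 100% | 66.4% |
| 2 | 8/10 = 80% | 44.4% to 97.5% | 8/8 = 100% | 63.1% |
| 3 | 7/10 = 70% | 34.8% to 93.3% | 7/7 = 100% | 59.0% |

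For example, 0.025^(1/8) = 0.631. With two failures, removal lifts the estimate by 20 percentage points and the lower limit by 63.1 − 44.4 = 18.7 points.

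**4. Could a count out of 10 discriminate at all?** For a rule of at least r successes, P(pass) = Σ C(10,k) p^k (1 − p)^(10−k), summed from k = r to 10. With r = 8 and p = 0.5 this is (45 + 10 + 1)/1024 = 5.5%. The true rates p are assumptions; the protocol gives none.

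| True rate | r = 8 | r = 9 |
|---|---|---|
| 50% | 5.5% | 1.1% |
| 60% | 16.7% | 4.6% |
| 80% | 67.8% | 37.6% |
| 90% | 93.0% | 73.6% |

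A rule that can fail is possible with 10 patients. The behaviour depends strongly on r, however, and nothing in the protocol favours one value.

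**The case against.** The strongest reply is that Section 4.0 does contain a criterion. A flat recording, or one whose only rise comes well outside the stated window, misses the benchmark. That stands. A reader might infer from the self-evident sentence that no outcome could ever count as not feasible; the benchmark sentence just before it rules that out for the individual patient. What is missing is a size for the rise and fall, and any result for the study as a whole.

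A reader might also infer that the judgement is made unmasked and after the fact. The protocol names no reader, no masking and no timing, so this would be inference from silence. The phrase about further analysis can likewise be read as a check of analysability that follows the benchmark. Even so, that check has no stated standard.

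It can be said that the tendon region, averaging interval and SD multiple belong in an analysis plan or imaging manual. Those numbers may well sit there. But the protocol is not merely silent: it states how sufficiency will be judged, and it is that statement which should change.

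It can be said that a 10-patient pilot whose images do not guide care needs no go/no-go count. That is fair. Reporting the observed proportion with an exact interval is a legitimate alternative.

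Finally, Section 14.0 records the reason for each withdrawal, so imaging failures could still be counted, and nothing says that they will be excluded. This is correct. The point is that the protocol leaves both readings open.

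One might try to size the problem by how often noise alone crosses a threshold. That would test single excursions rather than a rise and fall, and it would need frame-rate and noise figures that the protocol does not give. No such figure is relied on here.

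**Conclusion.** The point holds in a limited form and is a cheap improvement. The primary endpoint has a qualitative benchmark that an individual recording can fail. Sufficiency beyond that benchmark is left to impression, and no study-level result is defined as counting against feasibility. The one consequence that can be sized is the denominator: with two imaging failures among 10 and success in the rest, 80% (44.4% to 97.5%) becomes 100% (lower limit 63.1%). This assumes that all 10 patients reach imaging and that removed patients leave the analysis, which the protocol permits but does not state. The pass probabilities for 8 or 9 of 10 are illustrations at assumed true rates and recommend neither threshold.

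**What to change.** In Section 4.0, keep the benchmark and replace the self-evident sentence with a criterion fixed before the first case. For example:

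- A tendon region is drawn on the pre-injection frames.
- The one-second mean signal exceeds the mean of that recording's own 20 s baseline by a set multiple of its SD, for a set number of consecutive seconds, starting within the 10 to 40 s window.
- The signal then falls from its peak by a set fraction within the recording.

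Apply it to both the pre-takedown and the post-repair recordings, because the endpoint covers both, and report them separately. Section 2.0 expects perfusion to be lower after takedown, so a weak post-repair curve may be a true finding and should not be read as technical failure.

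State in Sections 4.0 and 14.0 that incomplete imaging counts as failure among all patients taken to imaging, whatever their withdrawal status. Report the proportion meeting the criterion (out of 10 if all reach imaging) with an exact 95% CI. If a go/no-go count is wanted, the sponsor should choose and justify it in advance. The team's impression can be kept as a secondary description.

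The cost is protocol wording and a short script run on video already planned, with no extra procedure for patients. The downside is that a fixed cut-off may class a few borderline curves as failures that the team would have accepted.
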